## 9.6 Subgroup Analyses for Primary and Secondary Endpoint

Analyses of time to alleviation of symptoms (Section 9.1.1.1, 9.1.1.2, Kaplan-Meier curve, the median time to alleviation of symptoms and its 95% CI) will be presented for the following subgroup 1), 2), 3) and 4).

Subgroup analyses will be performed for the ITTI Population in the following subgroups.

1) Total score of influenza symptoms at baseline

- $\leq 11$  points
- $\geq 12$  points

Stratified Peto-Prentice's generalized Wilcoxon test with region (Japan/Asia or Rest of the world) as stratification factors will be applied.

2) Region

- Japan/Asia
- Rest of the world

Stratified Peto-Prentice's generalized Wilcoxon test with composite symptoms score at baseline ( $\leq 11$  or  $\geq 12$ ) as stratification factors will be applied.

3) Body weight

- $< 80$  kg
- $\geq 80$  kg

4) Influenza virus type based on RT-PCR

- A/H1pdm
- A/H3
- B

5) Time to treatment from flu onset

- 0 hours  $\leq$  to  $\leq 24$  hours
- 24 hours  $<$  to  $\leq 48$  hours

Analyses of time to alleviation of symptoms (Section 9.1.1.1, 9.1.1.2, the median time to alleviation of symptoms and its 95% CI) will be presented for the following subgroup 5) and 6).

6) Meals before and after dosing

- Dosing > 4 hours before or > 4 hours after food taken
- Dosing within 2-4 hours before or 2-4 hours after food intaken
- Dosing < 2 hours before or < 2 after food intaken

If a subject has had meals both before and after dosing, the priority will be given to a category closer to the time of dosing. If multiple applicable categories exist even under this condition, data obtained before dosing will be adopted.

7) Age

- < 18 years
- ≥ 18 years

For the proportion of patients positive for influenza virus titer/RT-PCR, change from baseline in virus titer/amount of virus RNA (RT-PCR), area under the curve adjusted by baseline in virus titer/RT-PCR and time to cessation of viral shedding by virus titer/RT-PCR, these analyses will be presented for the following subgroup 8). Analyses of intrahouse infection rate will be presented for the following subgroup 8)

8) Influenza virus type and subtype based on RT-PCR

- A/H1pdm
- A/H3
- B

For the proportion of patients positive for influenza virus titer, change from baseline in virus titer for the following subgroup 9).

9) Influenza virus type and subtype based on RT-PCR

- A/H1pdm
- A/H3
- B

## 10. SAFETY EVALUATION

The following analyses will be performed in the safety population.

### 10.1 Adverse Events

AEs will be classified by system organ class and preferred term using Medical Dictionary for Regulatory Activities (MedDRA) Version 19.1. Of reported AEs on the eCRF, AEs reported after the initial dose of study drug will be used for safety analyses.

- 1) The number and proportion of patients who experienced at least 1 AE will be tabulated by treatment group. Their 95 % CIs will also be calculated with Clopper-Pearson method. In addition, the proportion will be compared with placebo group or oseltamivir group by using Fisher's exact test will be calculated. The number of events will also be tabulated. Death, other serious AEs, AEs

leading to withdrawal of the study drug, and treatment-related AEs will be summarized in the same manner as the overall summary of AEs. The definition of death, serious AEs, AEs leading to withdrawal, other severe AEs, treatment-related AEs are shown below.

Term	Definition
Death	AEs with “Fatal” in terms of outcome.
Other serious AEs (Serious AEs excluding death)	AEs with “Serious” in terms of seriousness excluding death
AEs leading to withdrawal of the study drug	AEs with “Drug withdrawn” in terms of the action taken for study drug.
Treatment-related AEs	AEs with “Related” in terms of the causal relationship with study drug.

- 2) The number and proportion of patients who experienced AEs will be tabulated by system organ class (SOC) and preferred term (PT) for each treatment group. For these summaries, patients with multiple AEs will be counted only once within an SOC and PT. Serious AEs, Treatment-related AEs and serious treatment-related AEs will be summarized in a similar manner. In addition, proportion of patients who experienced AEs of 2% or higher in any the dose treatment groups will be tabulated by SOC and PT.
- 3) The number and proportion of patients who experienced AEs in each category of timing of onset, severity, and outcome will be tabulated by SOC and PT for each treatment group. For these summaries, patients with multiple AEs will be counted only once by the highest priority shown in Table 4 within an SOC and preferred term. Treatment-related AEs will be summarized in a similar manner. The time-of-onset categories include Week 1 (1 to 7 days post-dose), Week 2 (8 to 14 days post-dose), and Week  $\geq 3$  ( $\geq 15$  days post-dose). Each AE will be classified into a time-of-onset category based on the number of days to onset which is calculated as (Date of AE onset – Date of dosing + 1). If a subject experienced multiple episodes of the same AE at different times of onset, the subject will be counted once each in the relevant time-of-onset categories.

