### **4.2 Allocation Procedure**

Patients in 20 to 64 years age stratum will be randomized on a 2:2:1 basis to S-033188 group, oseltamivir group, or placebo group. Patients in 12 to 19 years age stratum will be randomized on a 2:1 basis to either S-033188 group or placebo group. An interactive response technology (IRT) will be used to assign patients to numbers for which treatment has already been randomly assigned. The randomization will also be stratified by region

(Japan/Asia, Rest of the world), body weight (< 80 kg, ≥ 80 kg) and baseline composite symptom score (≤ 11, ≥ 12).

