## 5. ANALYSIS POPULATIONS

### 5.1 Efficacy Populations

The definitions of the Intention-To-Treat-Infected (ITTI) Population and the Per-Protocol Set (PPS) as efficacy populations are provided below. In this study, the ITTI Population is the primary analysis population. The PPS is the secondary analysis population, and data from the PPS will be used to perform a sensitivity analysis for the primary analysis.

The following analysis populations will be analyzed for this study based on enrolled patients with GCP compliance:

1) ITTI Population

This population includes all patients who receive the study drug with a confirmed diagnosis of influenza virus infection. Confirmation of influenza virus infection will be based on the results of RT-PCR on Day 1. The population will be analyzed according to the treatment to which the patients were randomized.

2) Per-Protocol Set (PPS)

This population includes all subjects included in the ITTI Population and did not meet any of the following conditions:

- Ineligible subjects
- Subjects with non-compliance of treatment
  - Treatment compliance rate is less than 60%. The definition of treatment compliance rate shown in 8.1 will be used.
- Subjects with inadequate follow-up
  - Subjects have no symptom data after initial treatment
- Subjects with prohibited medication
- Subjects with incorrect treatment allocation

3) Safety population

This population includes all randomized patients who receive at least one dose of the study drug. The population will be analyzed according to the initial treatment that the patients actually received.

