## **7. DEMOGRAPHIC VARIABLES AND OTHER BASELINE CHARACTERISTICS**

### **7.1 Subject Disposition**

- 1) Among all randomized subjects, the numbers of subjects who complete the study and subjects who discontinue the study will be tabulated by treatment group. For subjects who discontinue the study, reasons for withdrawal will also be tabulated by treatment group.
- 2) The number and percentage of subjects included in each of the ITTI and the PPS Populations among all randomized subjects will be calculated for the S-033188 group and Placebo group. For the subjects excluded from each population, the

reason for exclusion will be summarized. Fisher's exact test will be performed with a two-sided significance level of 0.15 to check differences among the treatment groups regarding the distribution of subjects in the ITTI and the PPS Populations. For the patients aged 20 to 64 years, the similar analyses will be applied in the S-033188 group and Oseltamivir group.

- 3) The number and percentage of subjects included in the Safety population among all randomized subjects will be calculated by prescribed treatment group. For the subjects excluded from the Safety population, the reason for exclusion will be summarized. For patients who receive at least one dose of the study drug, the treatment that the patients actually received will be defined as prescribed treatment. For patients who don't receive one dose of the study drug, the treatment to which the patients were randomized will be defined as prescribed treatment.

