## 7.2 Demographic and Baseline Characteristics

The following demographic and baseline characteristics among the ITTI and Safety Populations will be summarized using descriptive statistics for the S-033188 group, Oseltamivir group and placebo group. For quantitative data, the descriptive statistics will be calculated. For qualitative data, the frequency of each category and the percentage of subjects in each category among all subjects included in the analysis population will be presented.

For the patients aged 20 to 64 years in the ITTI Population, the following demographic and baseline characteristics will be summarized in the same manner.

- Continuous variable  
Age, height, body weight, BMI, total score of influenza symptoms and body temperature
- Categorical variable  
Age, body weight, sex, region, race, ethnicity, time to treatment from flu onset, presence or absence of flu vaccination, prior drug, prior therapy, medical history, smoking habits, presence or absence of meal before initial study treatment, duration between meal and administration (hours) (definition: absolute value of "time of dosing on Day 1" minus "time of meal obtained closest to the time of dosing on Day 1"), composite symptom scores, presence or absence of meal after initial study treatment, influenza virus subtype based on RT-PCR and influenza virus subtype based on RIDT (Rapid Influenza Diagnostic Test).

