## 8.3 Prior and Concomitant Medication

Prior and concomitant drugs will be coded using the World Health Organization (WHO) Drug Dictionary. Medication consists of drug and therapy. Prior medication is defined as all medications taken before Day 1 of study administration. Concomitant medication is defined as all medications taken on Day 1 or later. The drug and therapy can be also classified as both prior and concomitant.

For Safety population, the number of subjects who took prior drug and concomitant drug, and corresponding proportion will be summarized by WHO class and preferred term for each treatment group. For Safety population, the number of subjects who took prior therapy and concomitant therapy, and corresponding proportion will be summarized for each treatment group.

For ITTI Population, frequency of acetaminophen use will be summarized for each treatment group. Even though the date or time of acetaminophen use is missing, the frequency is counted. Wilcoxon rank sum test will be used to compare in frequency between the S-033188 group and the placebo or the Oseltamivir group. The two-sided significance level will be set at 0.15 in these analyses.

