## 9. EFFICACY ANALYSIS

In the ITTI Population that is the primary analysis population, the primary endpoint and all secondary endpoints will be analyzed. For the PPS that is a secondary analysis population, only the primary endpoint will be analyzed. Table 3 summarizes the primary

endpoint, secondary endpoints, other endpoints and statistical methods used to analyze these endpoints. The detailed statistical methods are described in later sections.

The analysis of each efficacy endpoint will consist of comparison between the S-033188 group (40 mg and 80 mg combined) and the placebo group using data of the two age strata pooled (i.e., 12 to 64 years age), and comparison between the S-033188 group (40 mg and 80 mg combined) and the oseltamivir group using data of 20 to 64 years age stratum.

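### The SAP's adverse-event tests of S-033188 against oseltamivir carry no 20 to 64 age limit, so about 96 S-033188 patients aged 12 to 19 with no randomised oseltamivir counterpart enter the comparison

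*SAP*

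**What the plan says.** Allocation differs by age. Adults aged 20 to 64 are randomised 2:2:1 to S-033188, oseltamivir or placebo. For the younger stratum, SAP 4.2 states: "Patients in 12 to 19 years age stratum will be randomized on a 2:1 basis to either S-033188 group or placebo group".

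The SAP acts on this in three places:
- **SAP 9 (efficacy)** compares S-033188 with "the oseltamivir group using data of 20 to 64 years age stratum".
- **SAP 7.1 (ITTI and PPS disposition)** says "For the patients aged 20 to 64 years, the similar analyses will be applied in the S-033188 group and Oseltamivir group".
- **SAP 7.2 (baseline)** adds a second set of summaries, "For the patients aged 20 to 64 years in the ITTI Population".

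The safety text has no such limit. SAP 10 opens with "The following analyses will be performed in the safety population", and SAP 5.1 defines that population: "This population includes all randomized patients who receive at least one dose of the study drug". SAP 10.1 item 1 then says that "the proportion will be compared with placebo group or oseltamivir group by using Fisher's exact test". It handles deaths, other serious AEs, AEs leading to withdrawal of study drug and treatment-related AEs in the same way.

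SAP 8.3 has the same omission for acetaminophen use in the ITTI population: "Wilcoxon rank sum test will be used to compare in frequency between the S-033188 group and the placebo or the Oseltamivir group", at a two-sided level of 0.15.

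SAP 10.5 repeats the AE analyses by age, but cuts at 18 years, not at the randomisation boundary of 20.

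**The concern.** Comparing safety with oseltamivir is a stated objective (Protocol 2.4, SAP 3.4). Followed as written, SAP 10.1 puts the 12 to 19 year-olds on the S-033188 side and none on the oseltamivir side. Part of any AE difference, or of its absence, could then come from the age mix and not from the drugs.

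Regimen is mixed in as well. The Protocol synopsis gives a 1-day treatment for ages 12 to 19 and 5 days for adults. AEs leading to withdrawal of study drug have little opportunity to occur after a single administration, so the younger patients would tend to dilute that rate on the S-033188 side only. For AEs overall the direction cannot be told from the documents.

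The SAP text contains no fully randomised safety comparison with oseltamivir. The age 18 subgroup leaves the 18 and 19 year-olds on one side only. Protocol 9.11.1 plans no between-group AE test from which a population could be carried over.

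**Working it through.** **Planned numbers.** Inputs are from SAP 2, 4.2 and 4.3.
- Randomised totals: the ITTI targets divided by the 65% RT-PCR positive rate give 93/0.65 = 143.1 (stated 144) and 875/0.65 = 1346.2 (stated 1350). The plan's figures reproduce, apart from rounding up.
- Adults: 1350 × 2/5 = 540 on S-033188 and 540 on oseltamivir.
- Ages 12 to 19: 144 × 2/3 = 96 on S-033188, 0 on oseltamivir.
- As written: 540 + 96 = 636 v 540, and 96/636 = 15.1%.

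**Bias in the S-033188 proportion.** With adult rate *p* and adolescent rate *q*, the pooled proportion is (540*p* + 96*q*)/636, so the shift is 0.151 × (*q* − *p*). Gaps of 5, 10 and 15 points give shifts of 0.75, 1.5 and 2.3 points.

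**Effect on the test.** This is the exact rejection probability of two-sided Fisher at 0.05, by full enumeration, with no drug effect and oseltamivir n = 540. The adult rates (20%, 25%, 30%) and the gaps, taken in both directions, are assumptions. Each cell is the range over these.

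| Comparison | No gap | 5-point gap | 10-point gap | 15-point gap |
|---|---|---|---|---|
| Ages 20-64: 540 v 540 | 4.19-4.29% | – | – | – |
| As written: 636 v 540 | 4.61-4.65% | 5.48-5.80% | 8.05-9.45% | 12.44-15.89% |
| ≥18 subgroup, 24 aged 18-19: 564 v 540 | 4.60-4.63% | 4.66-4.69% | 4.86-4.94% | 5.16-5.35% |
| ≥18 subgroup, 48 aged 18-19: 588 v 540 | 4.59-4.62% | 4.86-4.91% | 5.58-5.85% | 6.79-7.50% |

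The figure of 24 assumes an even spread over the eight ages 12 to 19: 96 × 2/8 = 24, or 24/564 = 4.3% of that side. The figure of 48 is a heavier case, 48/588 = 8.2%.

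The right reference for the second row is its own no-gap value. The step from about 4.2% to 4.6% comes from the discreteness of Fisher's test at equal arm sizes, not from age.

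**Withdrawals.** If both adult arms had 2% and the adolescents none (assumed), S-033188 would show 2% × 540/636 = 1.7%.

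**Acetaminophen.** In the planned ITTI population, 62/(350 + 62) = 15.0% of the S-033188 side is aged 12 to 19, against 0 of 350 on oseltamivir. No use counts are given, so the effect is not quantified.

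**Precision after restriction.** At an assumed 25% AE rate the 95% half-width for the difference is 1.96 × √(0.25 × 0.75 × (1/636 + 1/540)) = 4.97 points as written. For 540 v 540 it is 1.96 × √(0.25 × 0.75 × 2/540) = 5.17 points, about 4% wider.

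**The case against.** The best defence has four parts.

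1. **The inflation depends on assumed gaps.** This stands. The documents give no AE rates by age. With no gap there is no bias, and a 5-point gap adds only 0.8 to 1.2 points to the rejection rate. The 12-16% figures need a 15-point gap, which nothing in the documents supports or excludes.
2. **The ≥18 subgroup already limits the damage.** This largely stands. If ages are evenly spread it rejects at most 5.35% even with a 15-point gap. It remains a subgroup analysis, however. The main comparison keeps all 96 patients, and the subgroup is still not the randomised contrast.
3. **No decision depends on these p-values.** This is true. Type I error control in both documents concerns the primary endpoint. It limits the severity but does not excuse a partly non-randomised comparison for a stated objective.
4. **All ages is inferred from silence.** SAP 10.1 does not use those words, and SAP 9.1.1.2 also omits the limit for the efficacy comparison with oseltamivir. That section, though, is covered by the general statement in SAP 9, which reaches efficacy endpoints only. Nothing equivalent covers safety. The table shells are a separate document that was not available, and they may apply the filter. The SAP does not say so.

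The count of 96 is also not settled. Protocol 1.4 and 5.4 put ages 12 to 19 at about 15% of the whole study population, while 144/1494 = 9.6%. On the 15% reading, about 149 adolescents (0.15 × 1494 × 2/3) would join about 508 adults (0.85 × 1494 × 2/5), or 22.7% of the S-033188 side. So 96 is the lower figure.

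**Conclusion.** The concern holds and should be fixed. As written, the AE comparison with oseltamivir is 636 v 540, with 15.1% of the S-033188 side unable to have been randomised to oseltamivir. The bias is 0.151 times the age difference in AE rate. Under assumed adult rates of 20-30%, false-positive risk goes from 4.6-4.7% with no age difference to 5.5-5.8% at 5 points and 8.0-9.5% at 10 points. These figures rest on planned randomised counts and assumed rates, and the direction for overall AEs is unknown.

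The finding is certain as to the missing restriction in the SAP text, not as to how the tables were programmed. The primary analysis, the efficacy comparison with oseltamivir and the placebo safety contrast (2:1 in both age strata) are not affected.

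**What to change.** State in SAP 10.1 and 8.3 that S-033188 versus oseltamivir uses the 20 to 64 years stratum only, and that S-033188 versus placebo uses ages 12 to 64. Keep the all-ages S-033188 column as a descriptive summary. In SAP 10.5, add a 12-19 / 20-64 split beside the existing <18 / ≥18 split, without replacing it.

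The cost is wording and one filter on a stratum that the trial already randomises by, with no new data. About 96 S-033188 patients leave the oseltamivir contrast but stay in the placebo contrast. The loss of precision is the 4.97 to 5.17 points shown above.

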**Table 4 Priority of Categories**

Priority	Category		
	Severity	Outcome	Timing of onset (day)
1	Grade 5	Fatal	$\geq 1$ to $\leq 7$
2	Grade 4	Recovered/Resolved with sequelae	$\geq 8$ to $\leq 14$
3	Grade 3	Not recovered/Not resolved	$\geq 15$
4	Grade 2	Recovering/Resolving	
5	Grade 1	Recovered/Resolved	
6		Unknown	

- 4) AEs related hepatic disorders (SMQ code=20000006) will be listed.

## 10.2 Clinical Laboratory

- 1) For each of the hematological and biochemical test parameters, summary statistics of observed values and changes from baseline at each time point will be presented by treatment group at each scheduled time point.
- 2) For each of the hematological and biochemical test parameters, the plot of the baseline value and last observation value is presented for all patients. Last observation value is defined as the value at the last time point in all observed time points within acceptable window and the time point of early termination within acceptable window.
- 3) For each urinalysis parameter, the frequency of each category will be summarized by treatment group at each scheduled time point.
- 4) Each observed value will be classified into three categories: “within the normal range,” “higher than normal,” and “lower than normal.” The frequency of each category will be summarized by treatment group at each scheduled time point.
- 5) The number and proportion of patients who meet the pre-specified criteria shown in Table 5 will be presented by treatment group during the study. If a patient meet multiple criterion in all observed time points, the patient will be counted only once within the worst category.

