7.6.4.2 Routine Laboratory Tests

Routine hematology, blood chemistry, and urinalysis parameters (Table 7-5) will be measured by the clinical laboratory (see Section 7.6.4.5). Blood and urine samples for routine laboratory tests will be collected at Visit 1 (Day 1), Visit 4 (Day 5), Visit 6 (Day 15) and Visit 7 (Day 22) (or early termination).

Table 7-5 Routine Laboratory Tests

Category	Evaluation items
Hematology tests	Hematocrit, Hemoglobin, Platelet count, Erythrocytes (red blood cells), Leukocytes (white blood cells) with differential (eosinophil count, basophil count, neutrophil count, monocyte count, lymphocyte count)
Blood chemistry tests	Alanine aminotransferase (ALT), Aspartate aminotransferase (AST), Total bilirubin, Direct bilirubin, Indirect bilirubin, Alkaline phosphatase (ALP), Gamma glutamyl transpeptidase (GGT), Lactate dehydrogenase (LDH), BUN, Creatinine, Uric acid, Calcium (Ca), Chloride (Cl), Potassium (K), Sodium (Na), Total protein, Albumin, and C-reactive protein (CRP)
Urinalysis (Qualitative)	Glucose, Occult blood, Protein, and Urobilinogen

The investigator or subinvestigator will assess whether any abnormal changes from baseline (predose at Visit 1, Day 1) are clinically significant (see Section 7.6.5.6).

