**Table 2-2 Acceptable Time Windows for Parameters Other than Data from the Patient Diary**

Time Point	Acceptable Time Window
Pre-dose at Visit 1 (Day 1: Day -2 to Day1)	Predose from Day -2 to Day 1 for safety assessment
Pre-dose at Visit 1 (Day 1)	Predose on Day 1 for efficacy assessment
Post-dose at Visit 1 (Day 1)	QOL assessment with EQ-5D-5L questionnaire: by 0.5 hour post-dose on Day 1 Other measurements: 0.5 to 4 hours post-dose on Day 1
Visit 2 (Day 2)	Day 2
Visit 3 (Day 3)	Between Day 3 and Day 4
Optional-Visit 1 (Day 4)	Day 4
Visit 4 (Day 5)	Between Day 5 and Day 6
Optional Visit 2 (Day 6)	Day 6
Visit 5 (Day 9)	Between Day 7 and Day 11
Visit 6 (Day 15)	Between Day 12 and Day 18
Visit 7 (Day 22)	Between Day 19 and Day 25
Early termination	Date of early termination + 3 days

Measurements collected within the acceptable time window for each scheduled assessment time point, including data obtained at the time of withdrawal, will be used for the analyses of all endpoints at each assessment time point. For all patients with multiple measurements within a visit window, the measurement obtained closest to the target time point will be used. If two measurements collected with the same time deviation exist before and after the target time point, the measurement obtained before the target time point will be adopted for analysis. The assessment time point having no measurements within the corresponding acceptable time window will be considered as missing.

In the patient diary, if there are multiple measurements which may be adopted for a scheduled assessment, even though the above rules have been strictly followed, the measurements of the earlier assessment date or the earlier assessment time of day will be adopted (with the priority given to morning, followed by afternoon, evening, and bedtime, in this order). If multiple measurements collected with the same time (date and hour) for body temperature, the highest measurement will be adopted.

In the assessment of items from other than the patient diary, if there are multiple measurements which may be adopted for a scheduled assessment time point (even though the above rules have been strictly followed), the measurements at the time point entered in the CRF will be adopted.

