**Table 5 Pre-specified Criteria**

Term	Criteria
ALT (U/L)	$\leq 3 \times \text{ULN}$ $>3 \text{ to } \leq 5 \times \text{ULN}$ $>5 \text{ to } \leq 20 \times \text{ULN}$ $>20 \times \text{ULN}$
AST (U/L)	$\leq 3 \times \text{ULN}$ $>3 \text{ to } \leq 5 \times \text{ULN}$ $>5 \text{ to } \leq 20 \times \text{ULN}$ $>20 \times \text{ULN}$
Total Bilirubin (mg/dL)	$<1.5 \times \text{ULN}$ $\geq 1.5 \text{ to } <3 \times \text{ULN}$ $>3 \text{ to } \leq 10 \times \text{ULN}$ $>10 \times \text{ULN}$
AST (U/L) or ALT (U/L)	$\leq 3 \times \text{ULN}$ $>3 \text{ to } \leq 5 \times \text{ULN}$ $>5 \text{ to } \leq 20 \times \text{ULN}$ $>20 \times \text{ULN}$
AST (U/L) or ALT (U/L) and Total bilirubin (mg/dL)	Meet all of the following criteria: 
 
• AST <math>> 3 \times \text{ULN}</math> or ALT <math>> 3 \times \text{ULN}</math>
 
• Total bilirubin value <math>> 2 \times \text{ULN}</math>
 

ULN = upper limit of normal.

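### The worst-class liver-test count in SAP 10.2 5) has no post-dose limit, so read literally it includes the predose Day 1 sample; separately, Table 5 gives no class to total bilirubin of exactly 3 x ULN

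*SAP*

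**What the plan says.** SAP 10.2 5) plans the number and proportion of patients meeting the criteria in Table 5, which "will be presented by treatment group during the study". The counting rule follows: "If a patient meet multiple criterion in all observed time points, the patient will be counted only once within the worst category". The item does not say whether the predose value is in or out.

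The sampling times are in Protocol 7.6.4.2: "Blood and urine samples for routine laboratory tests will be collected at Visit 1 (Day 1), Visit 4 (Day 5"), then Visit 6 (Day 15) and Visit 7 (Day 22) or early termination. The same section makes the first sample the baseline, since investigators judge whether "abnormal changes from baseline (predose at Visit 1, Day 1) are clinically significant". SAP Table 2-2 lists the predose visit as a time point of its own, with the window "Predose from Day -2 to Day 1 for safety assessment".

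For adverse events the SAP does write a limit (10.1): "AEs reported after the initial dose of study drug will be used for safety analyses".

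Table 5 classes total bilirubin, in multiples of ULN, as below 1.5; from 1.5 to below 3; above 3 up to and including 10; and above 10.

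**The concern.** A by-arm table of the worst liver-test class is read as a summary of what happened on treatment. If the predose sample can supply the worst value, a patient with ALT at 4 x ULN before the first dose whose later values are normal is counted in the class above 3 up to 5 x ULN, although the drug cannot have caused it. Such patients can enter: Protocol 4.3 excludes liver disorders but sets no ALT, AST or bilirubin threshold.

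In randomised arms these cases are expected in equal proportion. They push a ratio between arms towards 1, and any chance imbalance in them adds noise to the comparison. The wording also leaves room for two programmers to produce different tables from the same data.

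The bilirubin boundary is a different kind of slip. A patient whose worst value is exactly 3 x ULN belongs to no row, so the classes need not add up to the number of patients tested.

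**Working it through.** The plan gives no figure for this table, so there is none to reproduce. Three checks follow.

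**1. Does the written rule take in the predose value?** Routine laboratory samples are taken on Days 1, 5, 15 and 22 (Protocol 7.6.4.2). Day 1 is predose (same section). The SAP treats predose as a safety time point (Table 2-2). The count runs over every observed time point (SAP 10.2 5), and nothing in 10.2 removes Day 1. The literal reading therefore includes it. This is an inference from four passages, not a statement in the SAP.

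**2. Do the Table 5 classes cover every value?** Applying the boundaries as printed, in multiples of ULN:

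| Value | Class assigned |
|---|---|
| Bilirubin 1.5 | 1.5 to below 3 |
| Bilirubin 2.9 | 1.5 to below 3 |
| Bilirubin 3.0 | none |
| Bilirubin 3.1 | above 3 to 10 |
| Bilirubin 10 | above 3 to 10 |
| Bilirubin 10.1 | above 10 |
| ALT or AST 3, 5, 20 | exactly one class each |

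The only gap is bilirubin at exactly 3 x ULN. The combined AST/ALT and bilirubin row uses a bilirubin threshold of more than 2 x ULN and is not affected.

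**3. What would predose values do to an arm comparison?** All rates here are assumptions. Let b be the share of patients above a threshold before dosing, equal in both arms, and p the rate arising after dosing among the rest. The table would then show

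counted rate = b + (1 - b) x p.

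The difference between arms becomes (1 - b) times the post-dose difference, so it changes little; the ratio changes more. For b = 2% and p = 2% against 1%:

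- S-033188: 0.02 + 0.98 x 0.02 = 0.0396
- placebo: 0.02 + 0.98 x 0.01 = 0.0298
- ratio 0.0396 / 0.0298 = 1.33; difference 0.98 points

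Over a range of b:

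| b | Ratio, 2% v 1% | Difference (points) | Ratio, 3% v 1% | Difference (points) |
|---|---|---|---|---|
| 0 | 2.00 | 1.00 | 3.00 | 2.00 |
| 0.5% | 1.67 | 1.00 | 2.33 | 1.99 |
| 1% | 1.50 | 0.99 | 1.99 | 1.98 |
| 2% | 1.33 | 0.98 | 1.66 | 1.96 |
| 5% | 1.16 | 0.95 | 1.32 | 1.90 |

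For the noise, the planned arms follow from SAP 4.2 and 4.3: S-033188 has 1350 x 2/5 + 144 x 2/3 = 540 + 96 = 636, and placebo has 1350/5 + 144/3 = 270 + 48 = 318. At 2% v 1%, the standard error of the difference is:

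- b = 0: sqrt(0.02 x 0.98/636 + 0.01 x 0.99/318) = 0.79 points
- b = 2%: sqrt(0.0396 x 0.9604/636 + 0.0298 x 0.9702/318) = 1.23 points

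Chance imbalance in the predose cases alone has a standard deviation of sqrt(0.02 x 0.98 x (1/636 + 1/318)) = 0.96 points, about the size of the assumed 1-point effect. Because it is chance, it could mask a difference or create one.

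**The case against.** The other side has four good arguments.

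- **The SAP is silent rather than explicit.** A reader might infer that the SAP says predose values count. It does not. In 10.2 2) a last value taken over all observed time points is plotted against a separate baseline value, so the phrase need not always take in baseline. This stands: the defect is a missing limit, and predose inclusion is only the literal reading.
- **Other outputs cover much of the ground.** Results that change after exposure and meet the liver criteria in Protocol Appendix 5 are recorded as adverse events (7.6.5.6), and the combined transaminase and bilirubin criterion is a serious adverse event (7.6.5.7.1). SAP 10.1 tabulates post-dose events by arm and severity and lists hepatic events. SAP 10.2 also gives change from baseline and low/normal/high counts by visit, and a plot of baseline against last value. A reader might infer that the plan as a whole hides a liver signal; these outputs do not support that. They do not replace the table, though: an isolated value between 3 and 5 x ULN need not become an adverse event, a plot of last values misses a Day 5 peak that resolves, and none of them sets the Table 5 classes against baseline.
- **The size is assumed.** Protocol 4.3 excludes liver disorders, and 7.6.4.3 excludes known chronic hepatitis B and untreated hepatitis C, so predose prevalence should be low, though not necessarily zero. The difference in proportions barely moves. Table 5 is descriptive, with no ratio and no test planned. All of this stands and limits the severity.
- **The bilirubin gap has no link to dilution.** A reader might combine the two defects. They are independent: the gap affects one exact value and says nothing about pre-treatment abnormality.

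Requiring the transaminase and bilirubin values of the combined row to come from one sampling date, or moving the 1.5 x ULN boundary, would be preferences rather than corrections of an error.

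**Conclusion.** The concern holds as a minor point in two separate parts.

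First, SAP 10.2 5) sets no post-dose limit on the worst-class count. Followed to the letter, it mixes pre-treatment liver-test abnormalities into the by-arm counts, which would shrink the ratio between arms and add noise. How much cannot be found from the documents. For assumed post-dose rates of 2% v 1% and predose prevalence from 0.5% to 5%, the ratio of 2.00 would read as 1.67 down to 1.16, while the difference stays between 1.00 and 0.95 points. These figures assume equal predose prevalence in the arms and the same post-dose rate in patients with and without a predose abnormality.

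Second, Table 5 assigns no class to total bilirubin of exactly 3 x ULN.

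Neither part touches an efficacy conclusion or a planned test.

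**What to change.** In SAP 10.2 5), limit the worst-class count to values obtained after the first dose, up to Day 22 or early termination. Add a table by arm that sets the worst post-dose class against the predose class, so that pre-existing and new abnormalities are seen apart. In Table 5, close the bilirubin boundary, for example by writing the second class as >=1.5 to <=3 x ULN.

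The cost is a sentence of SAP wording, one filter in the program, one extra table and one changed symbol. No new data are needed, because the predose and post-dose samples are already scheduled.
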